3.9 Safety endpoints

The type of AEs and AE severity will be tabulated by treatment arm. The number and percentage of patients with at least one AE for each type will be presented. Severity will also be presented accordingly.

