2.3 Randomisation

After consent has been obtained, patients are randomly assigned (1:1) to groups via a web-based service using computer-generated code to either receive IV iron or placebo. Group assignment is stratified by site, baseline haemoglobin (< or \geq 100 g/L), and planned surgery (isolated coronary artery or single valve surgery, or combined/other), using a mix of randomly permuted blocks of different sizes.

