2.8 Power and sample size calculation

ITACS is a pragmatic clinical trial aligned to normal hospital pathways. Some preliminary information was available [7] to help calibrate the distribution of DAH90 in the control arm. The endpoint has a left-skewed distribution with a small spike at 0, essentially due to early deaths. Therefore, the sample was determined by simulations (B=10,000 replications) to detect a specific shift in the median DAH90 with power > 90% after accounting for loss to followup and non-compliance. Specifically, DAH90 was obtained by generating first hospital length of stay (LOS) using a lognormal distribution, truncating it at 86 days (allowing for a minimum of 4 days in hospital), and computing DAH90 as 86 minus LOS for 95% of the data on average. The remaining data (5% on average) was generated as 0 to represent a small spike as observed in the original data [7]. A sample size of n=1000 patients was enough to detect a change of 1.45 in the median days with 94% power using a Wilcoxon rank-sum test. This calculation is adjusted for 5% loss to FU and 10% crossover. Power is lower for median regression and depends on the bootstrap method employed to calculate the 95% CI; for instance 84% is obtained using the Markov chain marginal bootstrap [8] available in the R package.

3 Statistical analysis

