3.1 Analysis principles

• Analyses will be conducted on a modified intention-to-treat (mITT) basis i.e. patients will be analysed according to the treatment they have been originally assigned to provided data is available (treatment policy estimand).

- All tests are two-sided and the nominal level of type I error will be 5%.
- The primary analysis of the effect of treatment on the primary outcome and key secondary endpoints will be adjusted for the stratification factors of baseline haemoglobin and planned surgery, with region adjusted for as a proxy for site to avoid model convergence issues.
- Subgroup analyses will be carried out irrespective of whether there is a significant treatment effect on the primary outcome.
- No imputation of missing values will be carried out for a percentage of missing values less than 5%. When the proportion of missing is substantial (>5%), a sensitivity analysis for the primary endpoint based on inverse probability weighting will be carried out.
- Analyses will be conducted primarily using Stata or R software.

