3.7 Secondary outcomes

Continuous secondary outcomes (#1, 2, 3, 6, 12) will be analysed using multivariable linear regression possibly after transformation. The analysis will be adjusted for the baseline measurement of the outcome where available. Red cell transfusion units (#4), DAH to 30 days (#8) and length of stay outcomes (#7a, 7b) will be summarised with medians and interquartile ranges and with estimated differences between medians and their 95% CIs computed via quantile regression, and for the latter (#7a,b) with death prior to discharge set as the largest duration. Binary outcomes (#4, 5, 9, 10, 11, and safety endpoints) will be expressed as risk ratios and standard 95% CI using log-binomial regression or exact logistic regression to approximate these values when the number of events in either arm is fewer than 5. In case of convergence issues with log-binomial regression, log-poisson regression with robust standard errors will be used. Where possible, adjustment for region, baseline haemoglobin and planned surgery similar to the adjusted analysis for the primary outcome will be carried out in all the models above to be consistent with the primary outcome analysis.

Supplementary analyses of the binary outcomes to 30 days will be performed to take into account the competing risk of death. This will use cumulative incidence functions

with estimated incidence at 30 days, with the incidence compared across treatment groups using risk ratios with 95% CIs derived using the delta method.

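### Safety is reported only by assigned arm, with no table by infusion received, although the plan allows for 10% crossover; crossover in either direction would dilute a harm of iron

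*SAP*

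**What the plan says.** SAP section 3.1 sets one rule for all analyses: "patients will be analysed according to the treatment they have been originally assigned to". It labels this a treatment policy approach, requires only that data be available, and makes no exception for safety.

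Section 3.9 says of adverse events: "The type of AEs and AE severity will be tabulated by treatment arm". It does not say whether arm means assigned or received, so the rule in section 3.1 governs. Section 3.7 puts the safety endpoints through the same models as the efficacy outcomes: "Binary outcomes (#4, 5, 9, 10, 11, and safety endpoints) will be expressed as risk ratios and standard 95% CI". The SAP defines no safety population, as-received set or sensitivity analysis by treatment received.

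Section 2.8 says of the sample size: "This calculation is adjusted for 5% loss to FU and 10% crossover". It gives neither the direction of the crossover nor a split by arm.

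Three other sections bear on the point. Section 2.7.3 lists anaphylactoid reactions first among the safety endpoints. Section 2.4 collects adverse events when the study drug is given. Section 2.5 records non-trial IV iron among the prior and concurrent medications.

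**The concern.** Mixing the arms pulls an observed difference towards no difference. For a superiority claim this works against the sponsor, so it is an accepted price of analysing by assignment. For harm it works the other way and can make a drug look safer than it is. The plan allows for this dilution in the power for its primary outcome but gives no safety result that is free of it.

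Two mechanisms matter. A patient assigned to iron who is never infused, but who has data, stays in the iron-arm denominator and lowers its event rate. A patient assigned to placebo who receives iron has any reaction to that iron counted under placebo. At stake is a safety statement that is more reassuring than it should be, most of all for events closely tied to an infusion.

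**Working it through.** **The plan's own figure.** The 10% enters one calculation only: "A sample size of n=1000 patients was enough to detect a change of 1.45 in the median days with 94% power". That power can be neither confirmed nor refuted, because the median and spread of the lognormal length of stay are not given. Simulation of the described model used 475 per arm after 5% loss, a two-sided 5% level, assumed medians of 6 to 10 days and assumed log-SDs of 0.5 to 0.8. Power ran from about 57% to 100%. A value near 94% is attainable: a median of 8 days and a log-SD of 0.6 with two-way crossover gave about 93%. The point below does not depend on this figure.

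**Dilution of the risk ratio.** Let p0 be the risk without iron, p1 = R × p0 the risk with iron, a the fraction of the iron arm not receiving iron, and b the fraction of the placebo arm receiving it. Assume that crossed-over patients carry the full risk of the treatment received and that crossover is unrelated to risk. Then:

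- observed iron-arm risk = (1 − a)p1 + a·p0
- observed placebo-arm risk = (1 − b)p0 + b·p1
- observed risk ratio = [(1 − a)R + a] / [(1 − b) + bR], in which p0 cancels
- share of the risk difference kept = 1 − a − b

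The SAP gives 10% without a direction, so each reading is shown. R is assumed.

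| Crossover | R = 2 | R = 3 | R = 10 | Risk difference kept |
|---|---|---|---|---|
| 10% of iron arm untreated (a = 0.1, b = 0) | 1.9/1 = 1.90 | 2.8/1 = 2.80 | 9.1/1 = 9.10 | 90% |
| 10% placebo to iron only (a = 0, b = 0.1) | 2/1.1 = 1.82 | 3/1.2 = 2.50 | 10/1.9 = 5.26 | 90% |
| 5% in each arm | 1.95/1.05 = 1.86 | 2.9/1.1 = 2.64 | 9.55/1.45 = 6.59 | 90% |
| 10% in each arm | 1.9/1.1 = 1.73 | 2.8/1.2 = 2.33 | 9.1/1.9 = 4.79 | 80% |

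For modest ratios the loss is moderate on every reading. For a strongly drug-linked event it is large only if placebo patients receive iron.

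**Effect on power.** Use 500 per arm (1000 allocated 1:1), a two-sided 5% level and 10% crossover in each arm, which is the worst row above. Event rates are not in the SAP and are assumed. Power ≈ Φ(|difference|/SE − 1.96), with SE = √{[p0(1 − p0) + p1(1 − p1)]/500}.

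- 5% v 10% (R = 2): 0.05/0.01658 − 1.96 = 1.06, power about 85%. Diluted to 5.5% v 9.5%: 0.04/0.01661 − 1.96 = 0.45, about 67%.
- 1% v 3% (R = 3): 0.02/0.00883 − 1.96 = 0.30, about 62%. Diluted to 1.2% v 2.8%: 0.016/0.00884 − 1.96 = −0.15, about 44%.

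**The case against.** The strongest reply is that nothing here is wrong or contradictory. Analysis by assignment suits a treatment policy approach, keeps the protection of randomisation, and is applied consistently in sections 3.1, 3.7 and 3.9. That stands. The assigned-arm safety results are legitimate, and the gap is only that they are the sole safety results.

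A reader might infer that the trial expects 10% of placebo patients to receive iron. The SAP does not support this. The 10% is a sample-size allowance, not a forecast, and section 2.8 also describes the adjustment as one for non-compliance, which fits untreated iron-arm patients at least as well. In that case no reaction to iron is booked to placebo, and a ratio of 2.0 falls only to 1.90.

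A reader might also infer that events such as hypophosphataemia can follow only the drug given. The SAP does not show this. Many of the listed safety endpoints are postoperative, such as transfusion reactions and surgical-site infection. For events at the blinded infusion itself, assigned and received treatment agree unless there is a dispensing error. What remains even then is the uninfused iron-arm patient in the denominator, and iron given later to a placebo patient.

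Finally, an as-received table can misattribute events too. If a placebo patient later given open-label iron were simply classed as iron, earlier events would be credited to iron. Section 2.5 mentions no dates for non-trial IV iron, and section 2.4 ties adverse-event collection to the study drug. This stands and shapes the fix.

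**Conclusion.** The point holds as a gap in the safety analysis, not as an error in the assigned-arm analysis. As written, the plan yields only safety comparisons that crossover in either direction would pull towards no difference. At the allowance in section 2.8, a true risk ratio of 2.0 would be seen as 1.73 to 1.90, depending on a direction that the SAP does not state. The risk difference would keep 80% to 90% of its size.

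These figures rest on the two assumptions stated above (full risk of the treatment received, and crossover unrelated to risk) and on crossover actually reaching 10%. If it is rarer, the dilution is smaller. The change is worth making before the data are analysed, so that the choice of a received-treatment table does not depend on the results.

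**What to change.** Keep the assigned-arm tables and risk ratios unchanged. Add to section 3.9:

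- a supplementary table of anaphylactoid reactions, adverse events by type and severity, and serious adverse events, by infusion actually received, restricted to patients who received a study infusion;
- a separate display for patients given open-label IV iron after a placebo infusion, with events attributed by their timing relative to that iron where dates are recorded;
- a statement that the table is supplementary because the comparison is not protected by randomisation.

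The cost is one extra set of tables. The inputs appear to be largely collected under sections 2.4 and 2.5, but the availability of dates for non-trial iron should be confirmed. The downside is possible confounding in the as-received comparison, which the label makes clear.

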3.10 Subgroup analyses

Pre-specified sub-group analyses will be conducted to assess the effect of IV iron on DAH90 by patient subgroups as indicated below:

- 1) age category (approximate quartiles)
- 2) sex (male/female)
- 3) surgery type (CABG/valve/TAVI/other)
- 4) iron deficiency (yes/no) where iron deficiency is defined as ferritin (<30 mg/dL, or ferritin <100 mg/dL and C-reactive protein >5 mg/L and/or transferrin saturation <20%)
- 5) haemoglobin strata ($\leq 100, 101-120, \geq 120 \text{ g/L}$)
- 6) study drug formulation (carboxymaltose / isomaltoside)
- 7) Time from randomisation to operation (<4 weeks or \geq 4 weeks).

Stratified effect estimates may be presented but the difference across subgroup will be tested via an interaction test in the corresponding median regression model for the primary endpoint. Forest plots will be constructed to illustrate results of the subgroup analyses.

4 References

[3] [EQ-5D-5L - EQ-5D [Internet]. Euroqol.org. 2021 [cited 18 March 2021]. Available from: https://euroqol.org/eq-5d-instruments/eq-5d-5l-about/

[4] WHO Disability Assessment Schedule (WHODAS 2.0) [Internet]. World Health Organization. 2021 [cited 18 March 2021]. Available from: https://www.who.int/classifications/international-classification-of-functioning- disability-and-health/who-disability-assessment-schedule

[8] He X and Hu F. Markov chain marginal bootstrap. J. Amer. Statist. Assoc. 2002; 97(459), 783-795.

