1.2 Purpose of the analyses

The purpose of this Statistical Analysis Plan (SAP) is to outline the pre-planned analyses to be completed to support the main publication of the ITACS study. Versions of the SAP will be tracked, with a clear distinction between changes before and after start of the statistical analysis.

2 Study design

ITACS is a multicentre, international, double-blind randomised clinical trial comparing the efficacy, safety and cost effectiveness of preoperative intravenous (IV) iron,1000 mg, single dose infusion given 1–26 weeks before the planned date of surgery) with placebo in patients with anaemia before elective cardiac surgery. The trial will incorporate the intervention into normal preoperative surgical pathways for hospital patients. The Trial is registered at ClinicalTrials.gov, Identifier NCT02632760, and the rationale/design article was published in the American Heart Journal in 2021 (doi.org/10.1016/j.ahj.2021.05.008).

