2.2 Patient population

As indicated in the protocol and reported in our rationale/design publication [2] patients must satisfy all the following inclusion criteria and none of exclusion criteria to be eligible to be randomised to the study

Inclusion criteria

- Adult (\geq 18 years) with anaemia (male or female Hb <130 g/L)
- Expected to undergo elective on-pump or off-pump cardiac surgery
- Able to receive trial drug 1- 26 weeks prior to planned surgery.

_

Exclusion criteria

- Transcatheter aortic valve implantation (TAVI) and other catheter laboratory interventional procedures
- Pregnancy
- Known hypersensitivity to study drug (ferric carboxymaltose, iron isomaltoside, or equivalent) or its excipients
- Previously documented TSAT >50%
- Previously documented vitamin B12 or folate deficiency
- Known or suspected hemoglobinopathy/thalassemia

- Bone marrow disease
- Hemochromatosis
- Renal dialysis
- Erythropoietin or IV iron in the previous 4 weeks

Note: Oral iron (tablets, capsules) therapy is not an exclusion criterion.

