2.6 Intraoperative characteristics

The type of surgery will be recorded and divided according to the following categories: CABG only, open valve surgery alone, TAVI alone, other surgery alone, CABG and Valve surgery*, CABG and Other surgery*, Valve and other surgery*, CABG, Valve and Other surgery* (TAVI being excluded for all categories indicated with *). Information on broader categories i.e. CABG, valve repair or replacement, TAVI, other will also be collected along with surgical LV grade (good (EF > 50%), moderate (EF 31–50%), poor (EF 21–30%), very poor (EF < 20%). Other standard characteristics related to surgery are also reported, revision surgery, number of distal anastomosis, total bypass time (min), minimum temperature during bypass (c°), IABP/ECMO/VAD post bypass, lowest haemoglobin concentration during CPB (g/L), inotrope infusion post bypass, cell salvage used during bypass, RBC and units given, platelets and number of units given, fresh frozen plasma (FFP) and number of units given. The total surgical time will be calculated from the first incision until the last suture is inserted.

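### Two subgroups in SAP 3.10, surgery type (with a TAVI level) and actual wait for surgery, appear to be defined after randomisation, so their interaction tests may be biased

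*SAP*

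**What the plan says.** SAP 3.10 lists seven subgroups for DAH90, each tested by an interaction term in median regression and shown in forest plots. SAP 3.1 runs them whatever the primary result. Three matter here:

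- Surgery: "surgery type (CABG/valve/TAVI/other". The section does not say whether this is the planned or the performed operation.
- Wait: "Time from randomisation to operation (<4 weeks or" longer. This is the interval that actually occurred.
- Product: "study drug formulation (carboxymaltose / isomaltoside". No rule is given for placebo patients.

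Four other places bear on these:

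- SAP 2.2 excludes "Transcatheter aortic valve implantation (TAVI) and other catheter laboratory interventional procedures".
- SAP 2.3 stratifies by "planned surgery (isolated coronary artery or single valve surgery, or combined/other", which gives two levels and no TAVI, and assigns patients "to either receive IV iron or placebo".
- SAP 2.6, on intraoperative data, states: "Information on broader categories i.e. CABG, valve repair or replacement, TAVI, other will also be collected".
- SAP 2 describes the infusion as "given 1–26 weeks before the planned date of surgery", so a planned date is part of the design.

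**The concern.** A subgroup interaction is a randomised comparison only if subgroup membership cannot depend on the treatment received. Operation performed and actual wait become known after randomisation, and usually after the infusion. Treatment could plausibly affect both. The trial's hypothesis (2.1) is that iron corrects anaemia before surgery, haemoglobin is measured preoperatively (2.5), and adverse events are recorded at drug administration (2.4). Any of these could lead a team to bring an operation forward, defer it or change it. If the patients so moved differ in prognosis, the arms within a subgroup are no longer comparable, and an apparent interaction can arise with no difference in treatment effect. The wait subgroup invites a reading about how early to give iron, so a spurious result there could mislead.

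**Working it through.** The SAP states no figure for this point, so there is none to reproduce. Three checks follow.

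**1. Surgery levels set side by side.**

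| Place | Levels | When known |
|---|---|---|
| 2.3 stratum | isolated coronary artery or single valve; combined/other | at randomisation |
| 2.6 broader categories | CABG; valve; TAVI; other | at operation |
| 3.10 subgroup | CABG; valve; TAVI; other | not stated |

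The 3.10 levels are those of 2.6. That the subgroup means the operation performed is an inference from this match, and a strong one, because planned TAVI is excluded at entry. A TAVI level can then hold only patients whose procedure changed later or who were entered in error. SAP 2.6 also has a finer list that gives combined operations (such as CABG with valve) their own categories. Section 3.10 uses the four broad levels and does not say where combined operations go.

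**2. Actual wait, illustrated by simulation under no treatment effect.** From the SAP: 1000 patients, 1:1 allocation, two-sided 5%, DAH90 as 86 minus length of stay, and about 5% zeros (2.3, 2.8, 3.1). Assumed, not from the SAP: lognormal wait with median 4 weeks and log SD 0.8; lognormal stay with median 8 days; a normal frailty score acting on log stay with coefficient 0.35, plus residual SD 0.35; frailer means a score above zero. A share *m* of frailer iron patients who would have waited under 4 weeks is moved to 4 weeks or more. That pool is 1000 × ½ × ½ × ½ = 125 patients.

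Interaction = (median difference, wait ≥4 weeks) − (median difference, wait <4 weeks). The spurious interaction comes from 2,000,000 simulated patients. The rejection rate comes from 2000 trials of 1000 patients, using the simulated standard deviation of about 0.66 days.

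| *m* | Patients moved | Spurious interaction (days) | Rejection rate at nominal 5% |
|---|---|---|---|
| 0% | 0 | −0.01 | 5.0% |
| 10% | 12.5 | −0.24 | 6.2% |
| 20% | 25 | −0.52 | 12.9% |
| 30% | 37.5 | −0.77 | 20.1% |

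At *m* = 20% the components are −0.24 (≥4 weeks) and +0.28 (<4 weeks), and −0.24 − 0.28 = −0.52. For scale, the trial was sized on a median shift of 1.45 days (2.8), and 0.52/1.45 = 36% of that. The sign follows from the assumed direction of movement.

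**3. Formulation.** Take the model columns 1, T, F and T×F, with T = 1 for iron and F = 1 for one of the two products.

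- Coded as received, F = 0 for every placebo patient, so T×F = F. Two columns coincide, the rank is 3 of 4, and the interaction cannot be estimated.
- Coded by a product assigned to both arms (for example, the one in use at the site), the rank is 4 of 4 and the interaction can be estimated.

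**The case against.** The best case for the plan is that post-randomisation membership does no harm by itself. Bias needs treatment to shift procedure or timing, and the shifted patients must differ in prognosis. If either condition fails, there is none. The trial is double-blind and runs within normal surgical pathways, which limits arm-specific rescheduling. At the mildest shift illustrated, rejection is about 6% against 5%. This stands, and it is why the point is a risk and not a demonstrated bias. It does not remove the risk, because blinding conceals allocation but not a haemoglobin result or a reaction.

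A reader might infer from the TAVI level that ineligible patients were to be analysed, or that the exclusion is flatly contradicted. The SAP does not support that. Exclusion applies at entry, 2.6 allows for TAVI among the operations recorded, and a patient whose procedure changes is still analysed as assigned. What remains is a nearly empty level that no eligible planned operation can fill. The CABG, valve and other contrasts can still be estimated.

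A reader might also infer that the formulation interaction can never be fitted. That is too strong. If product is set by site or country, placebo patients can be classed too. The SAP does not say how product is chosen, and the protocol, which is not at hand, may do so. The gap is a missing coding rule.

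**Conclusion.** The point holds as a risk in two of seven subgroup analyses. For surgery type it rests on the match between 3.10 and 2.6; for the wait it rests on the wording of 3.10 itself. The tests may be biased; the documents do not show that they are, and the size cannot be derived from them. The simulated rejection rates of 6% to 20% show the mechanism under assumed selective movement of frailer patients and are not estimates for this trial. The near-empty TAVI level and the missing place for combined procedures need correcting whether or not any bias exists. Formulation is a secondary point: the interaction is not estimable if coded as received, and estimable but open to confounding with site or region if mapped to both arms. The primary analysis of DAH90 in 3.6 does not use these variables as subgroups and is unaffected.

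**What to change.** Change the wording of 3.10 as follows.

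- **Surgery.** Define the subgroup by the planned-surgery stratum used at randomisation: isolated coronary artery or single valve surgery, versus combined/other. Split CABG from valve only if the planned procedure is recorded, which the SAP does not show. Delete the TAVI level. Combined procedures then have a level.
- **Wait.** Define the subgroup by the planned interval from randomisation to the scheduled surgery date, keeping the four-week cut. Show the actual interval as descriptive only. If the planned date is not recorded, keep the actual-wait analysis but label it exploratory.
- **Formulation.** Class both arms by the product in use at the site at randomisation, and acknowledge confounding with site or region. Add region terms only where they are estimable: if product follows region, a treatment-by-region term is aliased with treatment-by-formulation.

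The cost is SAP wording, a coarser surgery subgroup if only the stratum is available, and a planned interval that measures exposure time with more noise than the actual one.

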2.1 Objectives

Primary objective: To determine whether a single dose of IV iron (ferric carboxymaltose [Ferrinject[®]] or ferric derisomaltose [Monofer[®]] 1000 mg, given to anaemic patients before elective cardiac surgery improves the primary outcome (i.e.

days alive at home up to 90 days (DAH90) after surgery, a validated patient-centred outcome [1]).

Secondary objectives: To assess whether IV iron improves patient recovery because of correction of preoperative iron deficiency anaemia, reduced the need for blood transfusion and risk of complications, manifesting as earlier hospital discharge, lower mortality and reduced readmissions after surgery. We also aim to demonstrate that IV iron is cost-effective in this setting.

Study Hypotheses

Primary: A single dose of IV iron in the weeks before surgery corrects anaemia in patients undergoing elective cardiac surgery, and thereby improves patient recovery and their return to home when compared with placebo.

Secondary (Health Economics): Preoperative administration of IV iron will be 'dominant' when compared with current practice – that is, it will both save money and improve health outcomes.

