2.4 Baseline characteristics

Demographics are collected at baseline and include age, sex, weight (kg), weight (cm), ASA, and ethnicity (White/Caucasian, Indian/Pakistan, Asian, Black Other). Various laboratory parameters are also measured i.e. haemoglobin (g/L), creatinine (µmol/L), platelets, CRP (mg/L), Ferritin (ug/L), Transferrin (g/L), Serum Phosphate, (mmol/L), TSAT. A standard measure of health status, EQ–5D [3] is undertaken at baseline and is composed of 5 different domains with 5 questions per domain: mobility, self–care, usual activities, pain/discomfort; anxiety/depression. The EQ5D–VAS score is also collected. The WHODAS 2.0 assessment covering 6 domains of functioning [4] and the MacNew score [5] will also be calculated at baseline (prior to surgery). Finally, information on adverse events (AEs) is collected including AE severity (mild, moderate, severe), AE by system (neurological, cardiovascular, skin, other), SAE/SUSARs at the time of study drug administration.

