2.5 Preoperative characteristics

Pre-existing conditions or past events prior to surgery will be recording including smoking history, heart failure, chronic lung disease, diabetes, previous MI. Other standard pre-operative characteristics include 1) prior and concurrent medication i.e. ACE/ARB, β -blockers, Ca Channel blocker, statin, oral iron, IV parenteral iron, red cell transfusion; 2) laboratory parameters e.g. haemoglobin (g/L), haematocrit (L/L), creatinine (µmol/L), CRP (mg/L), ferritin (µg/L), transferrin (g/L), mean corpuscular volume [MCV] (fl), reticulocyte count(x10⁹/L, TSAT (%), platelets, TSH (mIU/L), free thyroxine T4 (pmol/L, alanine transaminase (ALT) (U/L), vitamin B12 (pmol/L), serum folate (nmol/L), GGT (U/L), serum phosphate (mmol/L). Finally, the risk of in-hospital mortality after cardiac surgery as evaluated by the EuroScore II [6] will also be measured preoperatively along with the following quality of life indicators: the functional status (measured by EQ-5D, 5 domains), EQ5D VAS score, the disability status (measured by WHODAS 2.0) and the MacNew score of Heart Disease Health-Related Quality of Life.

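### The iron-deficiency subgroup in SAP 3.10 has ferritin cut-offs in the wrong unit (a factor of 10,000) and an unbracketed and/or that leaves at least three classifications open

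*SAP*

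**What the plan says.** SAP 3.10 lists seven subgroups for DAH90. The fourth is iron deficiency (yes/no), defined by "ferritin (<30 mg/dL, or ferritin <100 mg/dL and C-reactive protein >5 mg/L and/or transferrin saturation <20"%. The only opening bracket stands after the word ferritin and closes at the end of the definition, so no bracket groups the conditions within it. For every subgroup, "the difference across subgroup will be tested via an interaction test in the corresponding median regression model for the primary endpoint". Under SAP 3.1 these analyses are done whether or not the primary result is significant.

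The laboratory lists use another unit for ferritin. SAP 2.4 (baseline) has "Ferritin (ug/L), Transferrin (g/L") and SAP 2.5 (preoperative) has "ferritin (µg/L"). No other section of the SAP defines iron deficiency. SAP 2.1 gives iron deficiency a role in the rationale: recovery is expected to improve "because of correction of preoperative iron deficiency anaemia".

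**The concern.** Two separate faults sit in one line.

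- **Unit.** The cut-offs are in mg/dL and the data in µg/L. If the rule is applied as printed, the subgroup variable may not divide the patients at all.
- **Logic.** The rule has the form A, or B and C and/or D. It can be bracketed in several ways that put the same patient in different groups.

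Entry to the trial depends on haemoglobin below 130 g/L (SAP 2.2), not on iron status, so the population can be mixed in this respect. This is the only one of the seven subgroups defined by iron status, and SAP 2.1 names correction of iron deficiency as the route to benefit. Readers will look at it. If the rule is still open when the data are unblinded, the subgroup is pre-specified in name but not in content.

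**Working it through.** The SAP gives no sample size, power or alpha for this subgroup, so there is no figure to reproduce. The check is a unit conversion followed by a comparison of the possible readings.

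**Step 1: unit.** Inputs: cut-offs of 30 and 100 mg/dL (3.10); ferritin recorded in µg/L (2.4, 2.5).

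- 1 mg/dL = 1,000 µg / 0.1 L = 10,000 µg/L
- 30 mg/dL = 30 × 10,000 = 300,000 µg/L
- 100 mg/dL = 100 × 10,000 = 1,000,000 µg/L

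The CRP unit in 3.10 (mg/L) agrees with 2.4 and 2.5, and transferrin saturation is a percentage in both 2.5 and 3.10. Only ferritin is out of line.

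**Step 2: effect if applied literally.** Write F for ferritin, C for CRP >5 mg/L and T for transferrin saturation <20%. On the natural reading, the comma and the following 'or' make the first limb sufficient alone. Ferritin values of 20, 60, 150, 1,000 and 5,000 µg/L were each crossed with C yes/no and T yes/no. Every profile is then deficient, because all five values lie below 300,000 µg/L.

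With S = 1 for everyone, the terms for S and for treatment × S in the median regression equal the intercept and the treatment term. The interaction coefficient is therefore not identified.

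**Step 3: effect after the unit is corrected.** With 30 and 100 taken in µg/L, three readings keep the first limb sufficient alone:

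- R1: F<30, or (F<100 and C), or T
- R2: F<30, or (F<100 and (C or T))
- R3: F<30, or (F<100 and C and T)

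| Ferritin (µg/L) | C | T | R1 | R2 | R3 |
|---|---|---|---|---|---|
| 20 | any | any | yes | yes | yes |
| 60 | no | no | no | no | no |
| 60 | no | yes | yes | yes | **no** |
| 60 | yes | no | yes | yes | **no** |
| 60 | yes | yes | yes | yes | yes |
| 150, 1,000 or 5,000 | any | no | no | no | no |
| 150, 1,000 or 5,000 | any | yes | **yes** | no | no |

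The readings are nested: everyone deficient under R3 is deficient under R2, and everyone deficient under R2 is deficient under R1.

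- R1 and R2 differ for patients with F ≥100 µg/L and T.
- R2 and R3 differ for patients with F from 30 to below 100 µg/L and exactly one of C and T.

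Correcting the unit therefore makes the variable usable but does not determine it.

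**The case against.** The strongest reply is that mg/dL is a labelling slip. The data are held in µg/L, so an analyst would apply 30 and 100 to that variable, or would see at once that one group is empty. This stands. The unit error is unlikely to bias anything silently, and a reader who infers that the subgroup test is void in practice goes further than the SAP supports. That outcome describes literal application only.

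Nor is it certain that literally every patient would be deficient. Two strained readings let the later conditions govern both ferritin limbs: (F<30 or (F<100 and C)) and T; or (F<30 or F<100) and (C or T). With mg/dL cut-offs, ferritin then plays no part and CRP and/or transferrin saturation alone decide the group. The variable would still divide patients, though not in a way that uses ferritin.

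A reader might also take this for the trial's key effect-modifier test. SAP 2.1 names the mechanism, but 3.10 does not rank its seven subgroups, and the trial's conclusion rests on the overall DAH90 comparison in 3.6.

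Timing invites a further inference. Ferritin, CRP and transferrin saturation appear at baseline (2.4) and again preoperatively (2.5), and secondary endpoint 2 in 2.7.2 measures change in ferritin and saturation after treatment. Someone might conclude that the iron arm would be classified by its own response. Nothing in 3.10 suggests this. Baseline values are the sensible default for a patient subgroup, and the protocol, not shown, may fix the time point. This is a request for clarification, not a defect.

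None of these replies resolves the and/or. The protocol may hold a clean definition, but 3.10 states its own without deferring to it.

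**Conclusion.** The definition is wrong as written and should be corrected. The unit contradicts SAP 2.4 and 2.5 by a factor of 10,000. On the natural reading, and assuming no recorded ferritin reaches 300,000 µg/L, the rule puts all patients in one group and leaves the interaction without an estimate. The lasting fault is the logic: with the unit repaired, at least three classifications remain, and the SAP does not choose among them.

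The number of patients whose group depends on the reading cannot be derived, because the SAP gives no distribution of ferritin, CRP or transferrin saturation. The effect on the subgroup estimate is therefore of unknown size. The scope is limited to one of seven subgroup analyses. The primary estimate, its confidence interval, the sample size, the interim boundaries and the secondary endpoints do not use this definition.

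**What to change.** Amend subgroup 4 in SAP 3.10 before unblinding:

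1. State the ferritin cut-offs in the recorded unit, µg/L.
2. Write the rule with explicit brackets so that only one reading is possible, and reconcile it with the protocol.
3. As a clarification, state that pre-dose baseline ferritin, CRP and transferrin saturation are used.

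A sensitivity analysis under another reading is optional; once one reading is fixed in advance it is not needed. The cost is one line of text under the version tracking that SAP 1.2 already provides, with no new data and no change to the primary analysis.
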